Participants. 120 older individuals using the aforementioned applications at the Brookline Senior Living communities, the largest owner and operator of senior living communities across the United States (1000+ communities, 100,000+ residents) where the average age of residents are 85 years old. With respect to study interest across each community, we have reached out to the resident directors at each non-demented community to gauge interest in this program: 84% of the resident directors believed at least some of their constituents would be interested in participating, with 73% of these respondents estimating between 1-10 individuals per site. Given that this is a feasibility study assessing: i) working with this seldomly studied population, ii) the implementation of mobile technology in a senior living community, and iii) the utility of a cognitive assessment that prescribes a personalized intervention regimen, an initial foray into this population with such an approach is well positioned for this particular R21 mechanism.

Markers of success. The primary aim of this pilot study is to gather information about the feasibility of utilizing this type of assessment/intervention combination in a senior living community to set up a future R01 application. To that end, our markers to assess feasibility will include: 1) how participating individuals and resident directors accept participating in this project, as assessed through exit surveys with each group, 2) how many eligible participants enrolled/participated/dropped out of this study, 3) what was the quality of the collected data (was there excessive missing/unusable data?), and 4) limited-efficacy testing to examine the expected degree of responsiveness to the two versions of the intervention.

Sample size. A power analysis to determine the needed sample size for this study resulted in us having to recruit a minimum of N=120 (40 in each condition) to achieve a balanced factorial design, which should be quite attainable given the interest indicated by the resident directors. Assuming 25% attrition, our recruitment plan will yield 90 participants, which will allow us to assess changes in performance as a function of training. Given the number of primary comparisons (3 scores of cognitive control at 2 time points (Pre- and Post-training)), there would be 95% power to reveal a group X session interaction on any given outcome, even with only 90 total participants split across the 3 groups. This corresponds to a medium effect size of .53, which is reasonable for a feasibility study of this size given the study-associated logistics. Pre- and post-training outcome data will be modeled using mixed within- and between-subjects GLMs and multivariate regressions¹⁰⁹. Significant interactions will be interrogated with appropriate follow-up tests between each group, including the direct assessment of effect size comparisons calculated using Satterthwaite's approximation¹¹⁰.

[figure not shown]
The goal of this R21 is to test the feasibility of deploying a targeted digital health remediation program for older adults in senior living communities based upon an initial characterization of these abilities. Below we discuss the logistics towards realizing this goal.

Mixed Model Approach. Here we propose to use a sequential exploratory mixed method design¹¹⁵⁻¹¹⁹ for this pilot study. Specifically, a quantitative design will be used to: (1) collect descriptive information regarding older adults' perceptions of each app to enhance the UX experience for this particular population to explore the feasibility of self-administration for cognitive assessment and remediation, and (2) make pre-, post-, within- and across-group comparisons of cognitive functioning based on neurocognitive test performance and self-rated assessments. The qualitative approach will begin with local semi-structured interviews regarding the use of each app, first in a group of 10 one-on-one sessions with seniors led by our UX testing consultant (see **Letter of Support**), followed by subsequent interrogation by senior-centric UX group testing group (Longevity Explorers™, see **Letter of Support**) whose members are seniors trained in UX design refinement. Using data gathered from these experiences, we will augment the UX design of each app for subsequent dissemination to the Brookdale Senior Centers for use. Brookdale participants will be asked questions about their experience following training, with feasibility of program participation assessed quantitatively by measuring the number and percentage of sessions completed per participant. Questions at this time point (previously used by Hill and colleagues⁹⁰) will include "Do you feel your everyday thinking abilities have changed from doing the computer exercises and, if so, how? 2. What did you like about doing the computer exercises? 3. What did you dislike about doing the computer exercises? 4. Now that the study is over, would you keep doing the computer exercises?" Responses during said interviews will be transcribed, with frequency tallies of response consistencies per question across participants being tabulated. We will perform thematic analyses for the identification of important patterns/themes⁹⁰, creating a coding framework that maximizes coherence amongst categories emerging from the qualitative data¹²⁰⁻¹²².

Protocol. Following the initial local UX testing, a convenience sample of 120 older adults will be recruited from throughout the Brookdale Senior Centers throughout the United States (see **Figure 3**; see **Recruitment and Retention Plan** for additional participant enrollment details). These individuals will be asked to complete the battery of tasks on the ACE platform (~45min) to characterize cognitive control abilities before and after the assigned intervention. Following their initial assessment, each participant will be randomly assigned (using a pseudo-randomized blocked design using blocks of 9 to ensure equivalent representation across groups) to a one of three intervention types: directed training (DT) on the ACCT platform, non-directed training (nDT) on the ACCT platform, or an expectancy-matched placebo control platform (PC). We will ask each resident director and their residents to refrain from discussing their assigned intervention with other communities to preserve blinding across sites. The total training experience will encompass 6 weeks of training (3 days/week), with each training session lasting 36 minutes (not including self-paced breaks). Each participant in the DT and nDT groups will engage in 12 3-minute blocks of submodules in each training session on the ACCT platform. However, those in the nDT group will play each of the three submodules 4 times equally, while participants in the DT group will play 12 blocks proportionally weighted towards the cognitive control domain(s) that are most deficient at baseline as determined by their baseline ACE performance, and thus most likely to benefit from directed training. For example, if (following the ACE assessment) a given individual shows deficiencies on their attention and working memory scores but normal performance in their goal-management abilities, they will be prescribed 5 training runs of the attention & working memory modules and only 2 of the goal management module. Customization of each DT participant regime will be accomplished via a web portal at UCSF that transmits personalized training parameters directly to the individual's ACCT application. Each training program contains self-guided instructional videos and practice modules for each treatment, consisting of 6 weeks of training (3 days per week). Training sessions are linked, such that the next session begins at the level attained at the end of the previous session. Participants are provided two types of feedback: 1) real-time feedback – indicating whether the participant successfully detected or classified the target and 2) punctuated feedback – participants advance through a series of “levels” that are reported at the beginning and end of each run. We will provide weekly feedback about intervention use and performance improvement (in addition to daily in-app feedback), in support of its utility found in a recent survey¹²³: 79% of health app users indicated that periodic feedback about their app usage encouraged them to continue.

```

graph TD
    A["Pseudo-randomize individuals participants (9 per block design)"] --> B["DT"]
    A --> C["nDT"]
    A --> D["PC"]
    B --> E["ACE & Surveys  
Baseline"]
    C --> E
    D --> E
    E --> F["6 week of training"]
    F --> G["ACE & Surveys  
Follow-up"]
    G --> H["ACE & Surveys"]
    style A fill:#e0e0e0,stroke:#000,stroke-width:1px
    style B fill:#fff,stroke:#000,stroke-width:1px
    style C fill:#fff,stroke:#000,stroke-width:1px
    style D fill:#fff,stroke:#000,stroke-width:1px
    style E fill:#fff,stroke:#000,stroke-width:1px
    style F fill:#fff,stroke:#000,stroke-width:1px
    style G fill:#fff,stroke:#000,stroke-width:1px
    style H fill:#fff,stroke:#000,stroke-width:1px
    
```

Expectancy-Matched Placebo Control. The placebo control group (PC) will engage in a battery of three apps delivered in the same prescribed manner as the other two groups, which we hypothesize as based on our experience will have minimal positive impact on the cognitive abilities we are assessing: i) an app with 100 different logic games of varying difficulty and length, ii) a language-learning app with 10 language options, and iii) an app that offers a guided Tai Chi program. The total training experience here will also be for 6 weeks (3 days/week), with each training session lasting ~30 minutes where participants will be asked to use each of the submodules for 10 minutes (not including self-paced breaks). We have already determined that this approach generates matched expectancy of benefits compared to our training groups by questioning 100 naïve individuals to predict their expected improvement on each cognitive domain after training on these apps (see ¹²⁴ for details of expectancy testing). This revealed that placebo training generates equivalent expectations of improvement across each outcome measure as the DT group, thus serving as an effective placebo condition. Furthermore, initial pilot work examining transfer effects following training on this battery has shown no evidence of improved cognitive control with respect to attention or working memory abilities, supporting its utility as a placebo control.

Assessments. All OAs will complete assessments at two periods: baseline and immediately following the intervention. In addition to measuring transfer to benefits to cognitive control (using ACE), we will also assess transfer of gains to functionally-relevant outcome measures, notably the Everyday Cognition Scale (ECog) to assess their ability to perform everyday tasks that demand memory, language, visuospatial abilities, planning, organization, and divided attention^{125,126}. The ECog scale has been used in other cognitive interventions trials and proven to be sensitive enough to detect improvements in healthy OAs and differentiate OAs from mild MCI^{127,128}. This survey will be sent directly to participants via an automated email campaign from Qualtrics™, with help from local resident mentors to complete these surveys on the same devices. Other surveys sent through this mechanism will include: i) a customized survey assessing participant expectancy across groups to further explore possible uncontrolled placebo effects (see for a description of this approach), ii) distractibility (via the Cognitive Failures Questionnaire)¹²⁹, and general health and well-being (SF-36)¹³⁰.

Infrastructure Support. Brookdale has already established an elegant infrastructure for sending, tracking, and gathering information as needed across all of their communities. Brookdale has 100,000+ residents in 47 states, divided into 5 geographic divisions, with several communications channels that provide resources on a monthly basis for Resident Programs associates. Each geographic division is led by a Directors of Resident Programs Engagement who supports the Resident Programs Associates in approximately 200+ communities. Each division is divided into approximately 50 areas, with each area supported by a Resident Programs “mentor”, and this team of 50+ mentors directly interacts with 15-20 communities. Resident directors have agreed to assist community residents in downloading and providing in-person help for this study, with [name] running a distributed webinar for all resident directors to teach them about these tools prior to study launch. Telephone and email support by the study team will be provided throughout the training period, in addition to active onsite support via resident directors. Each app will be configured to wirelessly transmit data automatically to our secure HIPPA-compliant server at UCSF when each training session is completed, with a custom web-portal facilitating data tracking in real-time to monitor participant adherence and data quality.

Markers of success. The primary aim of this pilot study is to gather information about the feasibility of utilizing this type of assessment/intervention combination in a senior living community to set up a future R01 application. To that end, our markers to assess feasibility will include: 1) how participating individuals and resident directors accept participating in this project, as assessed through exit surveys with each group, 2) how many eligible participants enrolled/participated/dropped out of this study, 3) what was the quality of the collected data (was there excessive missing/unusable data?), and 4) limited-efficacy testing to examine the expected degree of responsiveness to the two versions of the intervention.

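### Is the claim of 95% power with 90 completers at an effect size of .53 unsupported because its inputs are not stated?

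*Combined protocol and SAP*

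**What the plan says.** The Sample size section presents a calculation as the basis for recruitment: "A power analysis to determine the needed sample size for this study resulted in us having to recruit a minimum of N=120", with 40 per condition. It allows for 25% attrition, leaving 90. It introduces the power figure with "Given the number of primary comparisons (3 scores of cognitive control at 2 time points (Pre- and Post-training", then states that "there would be 95% power to reveal a group X session interaction on any given outcome, even with only 90 total participants", and adds: "This corresponds to a medium effect size of .53". On the analysis it says "Pre- and post-training outcome data will be modeled using mixed within- and between-subjects GLMs", together with multivariate regressions, and that significant interactions lead to between-group follow-up tests with effect-size comparisons.

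The Assessments section fixes the number of sessions: "All OAs will complete assessments at two periods: baseline and immediately following the intervention". The Markers of success section makes feasibility the primary aim. Efficacy is the last of four markers, worded as "limited-efficacy testing to examine the expected degree of responsiveness to the two versions of the intervention".

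Nowhere do the documents state alpha or sidedness, how the several scores enter alpha, the pre-post correlation (or SD of change), the metric and standardiser of .53, or the assumed pattern of the three arm means.

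**The concern.** A power statement is checkable only if its inputs are given, and here five are missing. The number printed, .53, is close to what many readers would take as a standardised mean difference of about half an SD. Taken that way, as a between-arm difference in change, 30 per arm gives far less than 95% power under ordinary assumptions. Taken as Cohen's f, it gives more than 95%.

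The sentence is offered both as the basis for 120 recruits and as reassurance that 90 completers are enough. If the claim were simply false, the efficacy comparison could be seriously underpowered for the effect the sponsor has in mind, and a null interaction could be over-read when the follow-on grant is planned.

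**Working it through.** **Inputs from the documents.** Three arms, two sessions, 120 recruited, 25% attrition, power 95%, effect size .53. The attrition step is consistent: 120 × 0.75 = 90, or 30 per arm if losses are even.

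**Inputs assumed, because none is stated.** Alpha .05, .05/3 or .05/6; pre-post correlation r from .3 to .8; one arm differing from two equal arms. For a given largest between-arm difference, that pattern is the most favourable to the omnibus test.

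**Test.** With two sessions, the group by session interaction is a one-way ANOVA on change, with df 2 and 87 and noncentrality λ = 90 f², where f is in SDs of change. For one arm differing by d, f = d × √2/3 = 0.4714 d. The SD of change is √(2(1 − r)) single-session SDs.

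**Can the plan's figures be recovered?** The repeated-measures form uses λ = 2 × 90 × f²/(1 − r). The section counts 3 scores at 2 time points, which gives 6. Take f = .25, r = .5 and alpha = .05/6:

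- λ = 2 × 90 × 0.0625/0.5 = 22.5, and power = 95.07%.
- Converting f to a difference with one arm differing: .25 × 3/√2 = .530.

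Both printed numbers come out. The set is not unique: f = .25 with r = .3 and alpha .05 gives λ = 11.25/0.7 = 16.07 and 95.1%.

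**Other readings of .53**

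| Reading | Calculation | Power |
|---|---|---|
| SDs of change | f = 0.4714 × .53 = .250; λ = 5.62 | 54% at .05; 28% at .05/6 |
| Single-session SDs | f = .250/√(2(1 − r)) | r = .3/.5/.7/.8: 40/54/77/92% at .05 |
| Cohen's f on change | λ = 90 × .53² = 25.3 | 99.6% at .05; 97.3% at .05/6 |

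On the second reading, 95% needs r of about .82 at alpha .05 and .875 at .05/6.

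**What 95% power would mean in each case.** The f on change needed for 95% is .4215 at alpha .05 and .4993 at .05/6. In single-session SDs the detectable difference is (f/0.4714) × √(2(1 − r)):

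| Alpha | r = .3 | r = .5 | r = .7 | r = .8 |
|---|---|---|---|---|
| .05 | 1.06 | 0.89 | 0.69 | 0.57 |
| .05/6 | 1.25 | 1.06 | 0.82 | 0.67 |

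The set that recovers both printed figures is the r = .5 entry of the second row: 2 × .25/0.4714 = 1.06. On the same inputs, a true difference in change of .53 single-session SD has λ = 5.62 and power of about 27.5%. Simulation of 20,000 trials gave 95.2% for the 1.06 SD difference and 27.3% for the .53 SD difference.

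**The case for a change.** The case for amending the section is that even its best defence leaves a trap. If f = .25 at r = .5 is what was run, the printed figures stand, but a reader who takes .53 as half an SD of differential change is out by a factor of two. Limited efficacy is one of four markers, the study is meant to support a larger application, and the section itself uses the calculation to justify N. Writing down the inputs would take one paragraph.

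The factual part of this stands: the inputs are absent, and .53 should not be read as half an SD of differential change without knowing r and the metric.

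What does not follow is that the plan is in error. The section never says the 95% applies to a half-SD difference in change; that meaning is supplied by the reader. The low powers come from readings and correlations that are themselves assumed. The correlation, standardiser and arm pattern used for planning play no part in the planned models. A null interaction will be judged from the observed between-group effects and their precision, and the plan already provides for between-group tests and effect-size comparisons after a significant interaction.

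**Conclusion.** The 95% is not reproducible from the stated inputs, but it is not shown to be miscalculated. At least one conventional set of inputs, using the section's own count of six comparisons, gives 95.07% and .530 together. The arithmetic that can be checked, 40 per arm to 120 to 90, is right.

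The gap is in reporting. Across r = .3 to .8 and alpha .05 to .05/6, with one arm differing, the difference in change with 95% power runs from 0.57 to 1.25 single-session SD, and the text does not say where in that range the study sits. All those values of r and alpha are assumptions.

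Supplying the missing inputs might alter no printed number, and would alter neither N, the design nor the analysis. The primary aim is feasibility, and no decision rule in the documents depends on the 95%. Anyone planning the follow-on trial should ask the sponsor for the inputs before reusing the figure, and should not carry forward .53 as a half-SD differential change. No change to this plan is needed.

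### The pre/post ACE analysis names no baseline covariate and does not say that arm differences with intervals are always reported; one baseline-adjusted model per score would supply both, for a precision gain that the plan's inputs leave undetermined

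*Combined protocol and SAP*

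**What the plan says.** The Sample size section states that pre and post outcome data will be "modeled using mixed within- and between-subjects GLMs and multivariate regressions". The quantity it powers is the interaction: "there would be 95% power to reveal a group X session interaction on any given outcome", for three cognitive control scores at two time points. It gives an effect size of .53 but no metric, alpha, pre-post correlation or ratio of post to pre SD. On dropout: "Assuming 25% attrition, our recruitment plan will yield 90 participants". On comparisons between arms: "Significant interactions will be interrogated with appropriate follow-up tests between each group", and effect size comparisons are part of that follow-up.

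The Mixed Model Approach section plans to "make pre-, post-, within- and across-group comparisons of cognitive functioning based on neurocognitive test performance and self-rated assessments". No significance condition is attached there, but no model or interval is named either.

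The Assessments section fixes the design at two occasions: "All OAs will complete assessments at two periods: baseline and immediately following the intervention". The Protocol section puts ACE first: "Following their initial assessment, each participant will be randomly assigned". The flowchart that follows it draws randomization ahead of the baseline ACE box.

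Under Markers of success, the fourth feasibility marker is limited-efficacy testing of how strongly participants respond to the two training versions, in a pilot meant to prepare a larger application.

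**The concern.** There are two linked points. First, the only model term that the plan powers is the interaction. With two occasions this contrasts mean change between arms, which subtracts the whole baseline score instead of weighting it by how well it predicts the post score. Where that weight is below one, the change score carries avoidable noise. A covariate may be hidden in the multivariate regressions, but none is stated.

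Second, the fourth marker asks for a degree, which calls for an estimate with its uncertainty. The plan does not say whether arm differences and intervals are reported when the interaction is not significant. If they were not, the marker would have no number for that score when the test misses, and a number biased upward when it hits. Either would be a poor input to planning the next study.

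**Working it through.** **Inputs.** From the Sample size section: 120 recruited, 40 per arm, 25% attrition, effect .53, power 95%, three scores, two occasions. Not in the documents and therefore assumed: two-sided alpha .05; .53 in raw SD units with one arm differing, so arm means (.53, 0, 0); pre-post correlation r varied; equal pre and post SDs (set to 1) until step 5.

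**1. The plan's own figures.** 120 × .75 = 90, or 30 per arm, as stated. The 95% power cannot be reproduced without unstated inputs. Under the assumptions above, the noncentrality is 30 × (2/3)(.53²)/σ² = 5.618/σ², with change variance σ² = 2(1−r). Power on (2, 87) df reaches 95% at r = .824, where σ² = .352 and the noncentrality is 15.96. Other readings also land near 95%: with evenly spread means (.265, 0, −.265) it needs r = .868. So r of about .82 is one consistent value, not a known one.

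**2. Complete data.** The change-score variance is 2(1−r) and the baseline-adjusted variance is 1−r². Their ratio is (1−r²)/[2(1−r)] = (1+r)/2.

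**3. Likelihood mixed model keeping baseline-only participants** (40 baseline and 30 post per arm, random dropout). The interaction variance per arm is (1−r²)/30 + (1−r)²/40, against (1−r²)/30 adjusted. The ratio is 4(1+r)/(7+r). For an arm difference at r = .5, the variances are .0667 (change score), .0625 (unconstrained mixed model) and .0500 (adjusted). A baseline-constrained mixed model also gives .0500.

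**4. Results at 30 completers per arm.** Half-widths are for the 95% CI of one arm pair. Power is for the 2-df test.

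| r | Ratio, complete data | Ratio, mixed model | Half-width: change / mixed / adjusted | Power: change → adjusted |
|---|---|---|---|---|
| .3 | .650 | .712 | .607 / .580 / .490 | 40.4% → 58.1% |
| .5 | .750 | .800 | .513 / .497 / .445 | 53.9% → 67.1% |
| .7 | .850 | .883 | .398 / .390 / .367 | 77.3% → 84.0% |
| .8 | .900 | .923 | .325 / .320 / .308 | 92.0% → 94.5% |
| .824 | .912 | .933 | .304 / .301 / .291 | 95.0% → 96.6% |

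Simulation (100,000 trials per setting) supports this. Both estimators average .53 and both tests hold .050 under the null. Estimating the slope costs about one point of the variance gain (ratio .763 at r = .5 and .922 at r = .824).

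**5. Unequal SDs.** With post SD equal to k times baseline, the complete-data ratio is k²(1−r²)/(1+k²−2rk). At r = .824:
- k = 1.1: .3884/.3972 = .978, a 2% cut.
- k = 1.2: .4623/.4624 = 1.00, no gain.
- k = 0.8: .2055/.3216 = .64, a 36% cut.

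The large-sample ratio never exceeds 1.

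**6. If estimates were reported only after significance.** With a true difference of .53 at r = .824, the reported estimate averages about 1.03 times the truth. With a true difference of .265 at the same r, the change-score test is significant in 40% of trials and the reported estimate averages 1.45 times the truth.

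**7. Why test and estimates should share a model.** The unadjusted and adjusted tests give opposite verdicts in 2.5% of trials at r = .824 and in 20% at r = .5.

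**The case against.** The strongest reply is that this swaps one valid model for another for very little. At the correlation that matches the stated power, the half-width moves from .304 to .291, which would change no feasibility conclusion. The larger gains need a lower r, at which the stated power fails on this metric. The 9% also rests on equal SDs and vanishes at a post SD 1.2 times baseline. All of that stands, and it is why no single gain is claimed. It does not remove the case for the change, because the covariate is collected anyway and the cost is one degree of freedom per model.

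A reader might infer that the plan withholds arm estimates unless the interaction is significant. The documents do not support that. The Sample size section says what follows a significant result, not what is suppressed otherwise, and the Mixed Model Approach section plans across-group comparisons with no such condition. What stands is that no interval or model is committed to.

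A reader might also take the flowchart to mean that baseline was measured after allocation. The Protocol text says the opposite, and directed training is weighted by baseline ACE results. The drawing may be loose. Still, the two disagree, and the adjustment relies on baseline being unaffected by allocation.

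Finally, responsiveness to the two versions may mean each version's own pre-post change. Pairwise arm differences alone would then miss the marker. That objection is right, and the fix covers it.

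**Conclusion.** The point holds as an improvement in efficiency and reporting. It is not an error: the planned interaction test keeps its type I error rate and its estimate is unbiased, so nothing here supports calling the analysis invalid.

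Baseline adjustment is no less precise than the change score in large samples, apart from one degree of freedom. How much it helps is undetermined, because r, alpha, the metric of .53 and the SD ratio are not given. With equal SDs the variance cut is 25% at r = .5 and 9% at r = .82, or 20% and 7% against a likelihood mixed model. With unequal SDs at r = .82 the complete-data cut can shrink to nothing. A claim of a large gain would go beyond the documents.

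The reporting gap is real but narrower: the plan is silent on intervals and on what is reported after a non-significant interaction. These conclusions assume random dropout and a baseline unaffected by allocation.

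**What to change.** - For each of the three ACE scores, analyze the post score by assigned arm with that score's own baseline as covariate. Alternatively, use a mixed model with baseline means constrained equal across arms, which keeps baseline-only participants.
- Take the 2-df arm test and the DT−nDT, DT−PC and nDT−PC differences from that one model.
- Report those differences with 95% CIs and standardized effect sizes, naming the SD used, whatever the omnibus p-value. Label them as planning estimates, not as nine separate tests.
- Report the within-arm pre-post change with its 95% CI for DT and for nDT, so that the fourth marker has an estimate in either sense.
- State that these are the ACE part of the comparisons in the Mixed Model Approach section. The self-rated measures stay as planned.
- Reconcile the Protocol text with the flowchart on the order of baseline ACE and randomization. The baseline constraint depends on it most.

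The cost is wording, one degree of freedom per model, and a few more reported figures: 3 scores × 3 pairs = 9 differences and 3 scores × 2 versions = 6 changes. The power statement should then refer to the adjusted arm test, whose power was no lower at any r computed under equal SDs. N = 120 and data collection do not change.

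### Are the differences between the three arms left unreported when the group by session interaction is not significant?

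*Combined protocol and SAP*

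**What the plan says.** The analysis rules are in the Sample size section. The model comes first: "Pre- and post-training outcome data will be modeled using mixed within- and between-subjects GLMs and multivariate regressions". This carries no significance condition. The next sentence does: "Significant interactions will be interrogated with appropriate follow-up tests between each group, including the direct assessment of effect size comparisons calculated using Satterthwaite's approximation". The primary comparisons are described as "3 scores of cognitive control at 2 time points". With 90 completers, "there would be 95% power to reveal a group X session interaction on any given outcome", and "This corresponds to a medium effect size of .53". The metric of that effect size, the alpha level and the pre-post correlation are not given.

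Mixed Model Approach separately commits to "within- and across-group comparisons of cognitive functioning based on neurocognitive test performance and self-rated assessments", again with no significance condition, but it lists no contrasts or intervals.

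Markers of success (the same text appears twice) gives as its fourth feasibility marker "limited-efficacy testing to examine the expected degree of responsiveness to the two versions of the intervention". The purpose is to learn about feasibility "in a senior living community to set up a future R01 application".

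**The concern.** The only sentence that mentions effect sizes between arms has significant interactions as its subject. Read literally, a score whose interaction test fails would have no planned DT-nDT, DT-PC or nDT-PC estimate, and a score that passes would be reported on the strength of having passed.

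That matters more in a pilot than in a confirmatory trial. Degree of responsiveness is a quantity to be estimated, and the DT-nDT contrast is the one that isolates personalised weighting of the training. Estimates kept only when significant are too large on average when power is low. An R01 planned from them could be too small, although the documents do not say these estimates will size the R01.

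**Working it through.** **1. Does the text gate the estimates?** Three statements bear on this.

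| Where | What is committed | Condition |
|---|---|---|
| Sample size, model sentence | Pre/post data modelled within and between subjects | None |
| Sample size, next sentence | Follow-up tests and effect-size comparisons | Significant interaction |
| Mixed Model Approach | Comparisons within and across groups | None |

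A model with three groups and two sessions contains the arm differences in change as coefficients or simple contrasts. Fitting it produces them whatever the p-value. The conditional sentence governs follow-up testing, and nothing forbids reporting the rest. If the responsiveness marker means change within DT and within nDT, the sentence does not touch it.

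**2. The plan's own figures.** Attrition reproduces: 120 × 0.75 = 90, or 30 per arm if losses are even. The 95% power can be neither confirmed nor refuted without the metric, alpha and correlation. With alpha .05 assumed and F on 2 and 87 df:

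- .53 as Cohen's f on change scores: λ = 90 × .53² = 25.28, power 99.6%.
- .53 as a standardised difference, converted to f = .216 to .265, in the usual repeated-measures formula λ = f² × 90 × 2/(1 − ρ): power 73% to 89% at ρ = 0 and 96% to 99.6% at ρ = .5.
- .53 baseline SD as the true DT-PC difference, analysed as change: λ = 30 × Σ(mᵢ − m̄)² / [2(1 − r)]. This is the reading used below.

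In the third reading, the graded pattern (.53/.265/0) has Σ = 2 × .265² = .1405. The patterns with one arm working (.53/0/0) or both (.53/.53/0) have Σ = .53² × 2/3 = .1873. At r = .5 the divisor is 1, so λ = 4.21 and 5.62, with power 42% and 54%.

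**3. Size of the filter if only significant results were kept.** Simulation, 400,000 trials per scenario, 30 per arm, mean DT-PC among significant trials divided by the true .53. Each range runs from graded to one or both arms working.

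| r (assumed) | Significant | Ratio, raw difference | Ratio, standardised by sample SD |
|---|---|---|---|
| .5 | 42% to 54% | 1.42 to 1.29 | 1.43 to 1.30 |
| .7 | 64% to 77% | 1.21 to 1.12 | 1.22 to 1.13 |
| .8 | 82% to 92% | 1.09 to 1.04 | 1.10 to 1.05 |
| power set to 95% | 95% | 1.026 | 1.035 |

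The standardised ratio is slightly higher because dividing by a sample SD already gives .535/.53 = 1.009 with no filter.

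Power of 95% needs λ of about 16, which is a DT-PC difference of .894 change-score SDs (one or both arms) or 1.032 (graded). For .53 baseline SD that means r = 1 − .53²/(2 × .894²) = .824, or 1 − .53²/(2 × 1.032²) = .868.

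DT-nDT is not inflated if both arms work equally. In the graded case at r = .5 it averages .380 against a true .265.

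**4. Scores that would miss the step.** At exactly 95% power per score, at least one of three is non-significant with probability 1 − .95³ = 14% if independent, about 12% at a between-score correlation of .5, and 5% if perfectly correlated. This is ordinary type II error. It becomes lost reporting only if silence is read as withholding.

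**5. What unconditional intervals would show.** The 95% half-width for one contrast is t(87, .975) × √(2/30) × √(2(1 − r)) = 1.988 × .258 × √(2(1 − r)), which is .51, .40 and .32 baseline SD at r = .5, .7 and .8.

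**The case for a change.** The strongest case for a change is that it costs one sentence, needs no data, and removes later discretion over what to report. A pilot should deliver estimates with intervals, within-arm change cannot separate training from practice on a repeated ACE battery, and the omnibus test can miss the DT-nDT contrast. The 95% power cannot be verified, so lower power cannot be ruled out.

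Part of this stands. The reporting rule is unwritten, and unconditional estimates with intervals would be the safer input to any later sample-size work. But the argument treats a sentence about follow-up tests as if it controlled all estimation, and two unconditioned commitments say otherwise. An omnibus test before pairwise tests is conventional with three groups and limits false positives.

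Adding three contrasts for three scores means nine unadjusted 95% intervals beside the gated tests. Each excludes zero exactly when an ungated 5% test from the same model would reject, so they would need a descriptive label to avoid reopening what the kept sentence closes. Finally, the cited source for the Satterthwaite step is not available here, so whether that step is the main between-arm estimate or a secondary comparison cannot be settled.

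**Conclusion.** This is a small gap in specification that analysts would fill sensibly, and no change to the plan follows. The documents do not say how the three pairwise differences are reported after a non-significant interaction, but they do not withhold them, and the planned model supplies them.

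No bias is demonstrated. At the stated 95% power the filter is worth about 3% to 4% (1.026 raw, 1.035 standardised), and with .53 as Cohen's f it is negligible. The larger ratios, up to about 1.4, require .53 to be a difference in baseline SDs, a pre-post correlation near .5, true power of 42% to 54%, and an analyst who suppresses non-significant scores. The first three are assumptions the documents do not supply, and the fourth is not in the plan. All figures assume 30 completers per arm and alpha .05.
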